**2. \* Describe the study hypothesis and/or research questions. Use lay language whenever possible.**

There are three primary and three secondary endpoints under investigation in this study: (1) Employment status, (2) wage, (3) number of hours worked per week at 12 and 18-months post enrollment. In addition, the effect of the intervention on (5) social communication, (6) mental health, and (7) quality of life will be explored. Specifically, our hypotheses are:

Hypothesis 1: Young adults who participate in an employer-based employment training and placement program will demonstrate a higher rate of employment than those in the control condition.

Hypothesis 2: Young adults who participate in a work-based employment training and placement program will earn higher wages on average compared to those in the control condition.

Hypothesis 3: Young adults who participate in a work-based employment training and placement program will work more hours per week on average than those in the control condition.

Hypothesis 4: Young adults who participate in a work-based employment training and placement program will increase their social responsiveness skills compared to those in the control condition, as measured by the Social Responsive

Scale, 2nd Ed.

Hypothesis 5: Young adults who participate in a work based employment training and placement program will display lower anxiety and depression scores than those in the control condition as measured by the Behavior Assessment System for Children, 3rd Ed. Teacher Rating Scales – Adolescent version.

Hypothesis 6: Young adults who participate in a work based employment training and placement program will report higher quality of life scores than those in the control condition as measured by the Quality of Life Questionnaire.

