**5. \* Describe any potential for direct benefits to participants in this study:**

We anticipate numerous positive outcomes from this project. At a minimum, 38 youth with autism will engage in community-based work experiences that lead to a competitive employment job while transitioning from school to adulthood. There is no guarantee of direct benefit to all individual participants.

The control group participants will benefit from participation in the assessments during the research. By completing the Supports Intensity Scale, they will gain a better understanding of their skill development needs with respect to future employment.

**6. \* Describe any potential for direct social impact in this study . For example, any engagement with specific communities to respond to community-identified needs, or ways the study will strengthen the well-being of the specific communities if applicable:**

This study resulted in a significantly higher percentage of participants in the PS+ASD condition acquiring employment while participants who were initially assigned to the waitlist condition were unlikely to acquire employment. Further, the acquisition of employment was demonstrated to result in higher rates of independence and quality of life outcomes for participants who gained employment. This represents both an important research outcome and a critical outcome for military dependent and connected youth. This is also an important study for military families as they navigate the complexities of military life (frequent moves, wait lists for services, etc.) and supporting a youth with autism.

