View Behavior Assessment Scale in Children Adolescent Ages 12-21	5 30805_BASC3_TRS_A_RS_Form_FNL (1).pdf	0.01	9/21/2016 7:54 PM	[name]	Research Measure	Yes
View Support Intensity Scale	4 Support Intensity Scale.pdf	0.01	9/21/2016 7:53 PM	[name]	Research Measure	Yes
View 12 and 18 Month Script Version 1 9-21-2016	3 Twelve and Eighteen Months Data script.docx	0.01	9/21/2016 7:52 PM	[name]	Research Measure	Yes
View Draft Teacher Recruitment Letter	Letter to teachers recruitment 2016 version 1 9-21-2016.docx	0.01	9/21/2016 7:39 PM	[name]	Recruitment/Advertising	Yes
View Draft Treatment Acceptance Letter	Draft Treatment Acceptance Letter version 1 9-21-2016.doc	0.01	9/21/2016 7:37 PM	[name]	Recruitment/Advertising	Yes
View Draft Parent/Student Recruitment Letter	Draft Parent Recruitment letter version 1 9-21-2016.doc	0.01	9/21/2016 7:37 PM	[name]	Recruitment/Advertising	Yes
View Draft Open House Flyer	Draft open house flyer version 1 9-21-2016.doc	0.01	9/21/2016 7:35 PM	[name]	Recruitment/Advertising	Yes
View Draft Control Group Acceptance Letter	Draft Control Acceptance Letter version 1 9-21-2016.doc	0.01	9/21/2016 7:34 PM	[name]	Recruitment/Advertising	Yes
View [name] Biosketch	[name] Bio Sketch.doc	0.01	9/20/2016 4:34 PM	[name]	CV/Biosketch	Not Applicable
View [name] Biosketch	biosketch [name].doc	0.01	9/20/2016 4:34 PM	[name]	CV/Biosketch	Not Applicable
View [name] Biosketch	[name] biosketch (1).doc	0.01	9/20/2016 4:33 PM	[name]	CV/Biosketch	Not Applicable
View [name] Biosketch	Bio Sketch [name].docx	0.01	9/20/2016 4:32 PM	[name]	CV/Biosketch	Yes

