Based on available data and past testimonies, the employment rate of students who received Project SEARCH program varies from 60% to 90% across different states and sites. Our pilot study of students with ASD in the Virginia site ([name], [name], et al., in review) indicates that the employment rate upon completion of students with ASD in the intervention group is higher than those with ASD in the control group with 87% vs. 6.7% employed at completion. Given the sample size designated in this study, with 16 in the treatment group and 22 in the wait-list control group, the study will have greater than .80 power to detect a significant difference (at the two sided 5% level) between treatment and control groups when using Fischer's Exact Test. For the six continuous outcome variables (i.e., hourly wages, hours/week, Social Responsiveness Scale total score, Behavior Assessment System for Children t-score, and Quality of Life Questionnaire percentile score), the effect sizes from the pilot study were used to determine that 16 subjects in the treatment and control groups were sufficient. The smallest relevant between group effect size (d) was 1.37 and smallest within group effect size (d) was 0.63 ([name], Under Review). These moderate to large effect sizes were reduced to determine a minimum power of estimate of 80% for a sample size of 16 (N=32). The power analysis indicated that a between group effect size (d) of 1.10 with a sample size 16 (N=32) had 0.85 power (95%CL = 0.81 to 0.88) and a within group effect size (d) of 0.25 had 0.90 power (95%CL = 0.87 to 0.92) with alpha set at 0.05 when using a mixed model with SAS® PROC MIXED with three time points and two levels (SAS® v9.4, 2013). In this balanced design, power greater than or equal to .80 is often assumed to be adequate and acceptable to detect the difference of a given magnitude in the mean outcome for the two groups, holding the significance level (a = .05) constant.

We anticipate that the individuals providing information will include:

38 Individuals with ASD

38 Parents of individuals with ASD

20 Teachers of individuals with ASD

Total = 96

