**4. \* List the study inclusion criteria:**

In order to be selected for inclusion in the sample pool, participants must meet the following criteria: (1) A diagnosis of Autism Spectrum Disorder; (2) between 18 - 22 years of age; (3) entering final year of school participation and is on track to receive a diploma or a certificate; (4) meets eligibility requirements for vocational rehabilitation; (5) possesses independent personal hygiene, eating and grooming skills; (5) able to pass drug screen and felony check and have immunizations up to date (These items will be seen by the community business only as required by them for interns to be present at their work site); and (6) desires and plans to work competitively in the community at the conclusion of the 9-month program, (7) Be a military dependent or military connected youth.

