**See the help text for additional guidance**

This is a randomized, wait-list controlled study of the efficacy of the Project Search plus ASD Supports Model (PS+ASD) in 32 adolescents and young adults aged 18 to 22 with ASD. Approximately 32 subjects will be enrolled and randomized in a 1:1 ratio to treatment or wait-list control. A sufficient number of potential subjects will be screened to achieve this number of enrolled subjects.

The six dependent variables in question are the primary endpoint employment rate (upon completion and at 12 months and 18 months post-enrollment) and the secondary endpoints hourly wages, hours/week, Social Responsiveness Scale total score, Behavior Assessment System for Children 3rd Ed. Anxiety and Depression t-score and the Quality of Life Questionnaire percentile score at baseline (Baseline), 12 months post enrollment (12 months), and 18 months post-enrollment (18 months). The efficacy of the intervention will be analyzed by comparing the differences in these six variables between the treatment group and the control group.

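### Does filing the BASC-3 teacher form for ages 12-21 undermine the Hypothesis 5 T-score in a trial that enrols ages 18-22?

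*Combined protocol and SAP*

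**What the plan says.** Hypothesis 5, in Background, Rationale and Goals Q2 and again in Study Procedures Q1, compares anxiety and depression with the "control condition as measured by the Behavior Assessment System for Children, 3rd Ed. Teacher Rating Scales", adolescent version. Study Procedures Q6 names the variable, "Behavior Assessment System for Children 3rd Ed. Anxiety and Depression t-score and the Quality of Life Questionnaire percentile score", and sets the assessments at baseline, 12 and 18 months after enrolment. The sample-size answer (Study Population Q3) counts the "Behavior Assessment System for Children t-score, and Quality of Life Questionnaire percentile score" among the continuous outcomes. It plans a "PROC MIXED with three time points and two levels" analysis and states that "a between group effect size (d) of 1.10 with a sample size 16 (N=32) had 0.85 power".

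The filed research measure is titled "Behavior Assessment Scale in Children Adolescent Ages 12-21" in the document list. The inclusion criteria (Study Population Q4) read "2) between 18 - 22 years of age; (3) entering final year of school participation". No supplied section gives a norm table, an alternative form, a raw-score fallback, an exclusion or a missing-data rule for a participant older than the form's title allows.

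**The concern.** A T-score is a raw score placed against a reference sample, here one that the form's title limits to age 21. Eligibility exceeds that limit at entry, and follow-up widens the gap, so for some participants the stated variable may have no norm within the labelled range. The plan does not say what happens to them.

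There are two ways this could hurt. If the oldest norms are carried forward, the T-score loses its normed meaning for those people. If their scores are set to missing, Hypothesis 5 loses information in a trial of about 32. In either case the choice is left to an analyst who may already have seen data. One remedy would be to analyse baseline-adjusted raw anxiety and depression scores for everyone and keep T-scores for description only.

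**Working it through.** **The plan's own figure.** Inputs from Study Population Q3: d = 1.10, 16 per group, two-sided alpha 0.05. For a two-sample t-test the noncentrality is d / sqrt(1/n + 1/n) = 1.10 / sqrt(2/16) = 3.11 on 30 degrees of freedom. Power is 0.853, which reproduces the stated 0.85.

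**Who leaves the labelled range.** Read the title as running to the 22nd birthday. A participant is out of range when entry age plus elapsed time reaches 22:

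- at baseline: entry at 22 or over
- at 12 months: entry at 22 - 1 = 21 or over
- at 18 months: entry at 22 - 1.5 = 20.5 or over

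**How many.** The documents give no entry-age distribution, so this is a range under assumptions. For entry ages uniform from lo to hi, the share out of range at month m is (hi - (22 - m/12)) / (hi - lo), held between 0 and 1.

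| Assumed entry ages | Baseline | 12 months | 18 months |
|---|---|---|---|
| 18 to 20th birthday | 0 | 0 | 0 |
| 18 to 21st birthday | 0 | 0 | (21 - 20.5)/3 = 17% |
| 18 to 22nd birthday | 0 | (22 - 21)/4 = 25% | (22 - 20.5)/4 = 37.5% |
| 18 to 23rd birthday | (23 - 22)/5 = 20% | (23 - 21)/5 = 40% | (23 - 20.5)/5 = 50% |

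Of 32 participants, the last two rows leave 32 x 0.375 = 12 or 32 x 0.50 = 16 without an in-range score at 18 months. The first row leaves none.

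**If every score is kept.** Applying one conversion to all out-of-range participants treats the arms identically. Age at entry is fixed before randomization, so the share affected has the same expectation in each arm. No score is lost and no bias between arms is shown. The cost is interpretive: the T-score is not age-normed for those people.

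**If out-of-range scores were dropped (hypothetical; no section says so).** At 18 months, 16 x 0.625 = 10 or 16 x 0.50 = 8 per arm would remain. Ignoring earlier visits, the standard error of the contrast grows by sqrt(16/10) = 1.26 or sqrt(16/8) = 1.41. Noncentrality at d = 1.10 becomes 1.10 / sqrt(2/10) = 2.46 or 1.10 / sqrt(2/8) = 2.20, giving power 0.643 or 0.535.

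A three-visit mixed model also uses the in-range earlier scores. The calculation takes unit variance, equal correlation rho between visits, a common baseline mean, a generalised least squares standard error for the 18-month contrast, and a noncentral t with degrees of freedom equal to the expected number of 18-month scores minus 2. The values of rho are assumptions, since the documents give none.

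| rho | None dropped | Dropped, entry to 22nd birthday | Dropped, entry to 23rd birthday |
|---|---|---|---|
| 0 | 0.853 | 0.643 | 0.535 |
| 0.5 | 0.935 | 0.774 | 0.665 |
| 0.7 | 0.988 | 0.910 | 0.828 |

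The value 1.10 is itself a reduction. The same answer gives the smallest pilot between-group effect as 1.37. At that effect, dropping leaves power of 0.83 or 0.72 at rho 0, 0.92 or 0.84 at rho 0.5, and 0.98 or 0.95 at rho 0.7.

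**The case for a change.** The best case for a change is that no separate protocol was uploaded, and the Study Procedures Q6 prompt asks for methods detailed enough to be replicated. A rule that determines the Hypothesis 5 variable arguably belongs there. Without it an analyst could extrapolate norms, drop scores or mix the two. In a trial this small, dropping 12 or 16 people at 18 months would matter. Raw totals come from the same completed forms, cost nothing to collect and put everyone under one rule.

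The gap therefore stands as a fact; the need for a change does not follow from it. The same prompt asks for language suited to non-scientific committee members, which is not where norm-table detail is expected. The instruments description (Grant Attachment 10) and the form itself are listed but not supplied, so a rule may exist there. The power loss needs both an assumed age distribution and a dropping rule that nobody has written.

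The raw-score remedy is also not free. It gives up the normed metric for participants who are in range, possibly all of them, and does not validate the items above age 21. If baseline becomes a covariate, it also departs from the planned three-time-point model. Timing counts against it too. Background, Rationale and Goals Q6 already says "This study resulted in a significantly higher percentage of participants in the PS+ASD condition acquiring employment" and goes on to describe quality-of-life findings, so secondary data appear to have been analysed. Replacing a prespecified variable now would probably be post hoc.

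**Conclusion.** The age mismatch is genuine: the form's title stops at 21, eligibility goes to 22, and by 18 months anyone who entered at 20.5 or over is past the range. It does not call for a change. Under the age scenarios above, the share affected at 18 months runs from 0 to 50%, and the documents cannot narrow that. With all scores kept, the expected effect on the between-arm comparison is nil; what is lost is the normed reading of some T-scores. The falls in power are hypothetical because they depend on discarding data. The employment endpoint is untouched.

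What remains is an unwritten scoring detail on one secondary outcome. A competent analyst would score these forms by one convention, keep them, and report that convention with the number of participants past the range at each visit. A raw-score check could sit beside it, labelled post hoc if the data have been seen. Making raw scores the main Hypothesis 5 variable would exchange one imperfection for another.

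This rests on reading the title as running to the 22nd birthday, and on the title being the only evidence of the age limit. If the limit were the 21st birthday, the shares would be larger (62.5% or 70% at 18 months in the two wider scenarios). The reasoning would not change, because keeping the scores still preserves the comparison.

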#### COVID-19 Contingency Plans

During the COVID-19 Crisis, we will meet with families and teams via phone or video conference. We will not hold any face to face or in-person contacts. When ever we hold such a meeting, at least two research staff will participate on the phone or video conference. Also, our research staff, who may be working from home, will ensure that they are in a private room in their homes where other's cannot hear their conversations.

8. If applicable, describe alternatives (research or non-research) that are available to potential participants if they choose not to participate in this study:

The only alternative to participation in this study is not to participate.

If a student decides not to take part in the study, but is interested in work experiences like Project SEARCH, we will refer them to other similar programs if there are any in their locality.

**9. Upload any supporting tables or documents (e.g. protocol documents, figures/tables, data collection forms, study communications/reminders):**

Upload ALL instruments/guides that will be used or that participants will experience (i.e. see, hear, complete), including measures, scripts/questions to guide interviews, surveys, questionnaires, observational guides, etc.:

Upload ALL recruitment and screening materials, including such as ads, flyers, telephone or in-person scripts, letters, email invitations, TelegRAM announcements, and postcard reminders, screening scripts, screening forms, and screening measures:

Document Name	Document	Version	Date Modified By	Uploaded Type	Approved
View Student Assent Version 2 11/1/2017	Student Assent Clean Version 2 11-1-2017.pdf	0.06	4/15/2023 11:40 AM	[name] Consent/Assent/Information Not Sheet	Not Applicable
View Student Consent Version 10 11/22/2019	Student Consent 10 11-22-2019 clean version2.pdf	0.31	4/15/2023 11:40 AM	[name] Consent/Assent/Information Not Sheet	Not Applicable
View LAR Consent Version 10 11/22/2019	LAR Consent Version 10 clean version2.pdf	0.30	4/15/2023 11:40 AM	[name] Consent/Assent/Information Not Sheet	Not Applicable
View Educator Consent Version 10 clean 10 11/22/2019	Educator Consent Version 10 clean version2.pdf	0.30	4/15/2023 11:40 AM	[name] Consent/Assent/Information Not Sheet	Not Applicable
View COVID-19 Contingency Assent Form Individual Assent	Student Assent.pdf	0.03	4/15/2023 11:40 AM	[name] Consent/Assent/Information Not Sheet	Not Applicable
View COVID-19 Contingency Consent Form LAR Consent	LAR Consent.pdf	0.03	4/15/2023 11:40 AM	[name] Consent/Assent/Information Not Sheet	Not Applicable
View COVID-19 Contingency Consent Form Individual Consent	Individual Consent.pdf	0.03	4/15/2023 11:39 AM	[name] Consent/Assent/Information Not Sheet	Not Applicable
View COVID-19 Contingency Consent Form Educator Consent	Educator Consent.pdf	0.03	4/15/2023 11:39 AM	[name] Consent/Assent/Information Not Sheet	Not Applicable
View COVID-19 Contingency Protocol	COVID Contingency Protocol for CDMRP version 3.docx	0.03	6/8/2020 11:05 AM	[name] Other	Yes
View York County Closure Form	relying_site_closure York.pdf	0.01	8/31/2019 1:45 PM	[name] Non-VCU site submission form	Yes
View Williamsburg/ James City County Closure Form	relying_site_closure Williamsburg James City County-signed.pdf	0.01	8/31/2019 1:44 PM	[name] Non-VCU site submission form	Yes
View Hampton City Public Schools Closure Form	relying_site_closure Hampton.pdf	0.01	8/31/2019 1:43 PM	[name] Non-VCU site submission form	Yes
View New Horizons Closure Form	New Horizons Closure Report.pdf	0.01	8/31/2019 1:43 PM	[name] Non-VCU site submission form	Yes
View Newport News Public Schools Closure Form	Nwport News Public Schools Signed Relying Site Closure Notice.pdf	0.01	8/31/2019 1:42 PM	[name] Non-VCU site submission form	Yes
View Certificate of Confidentiality	Certificate of Confidentiality.pdf	0.03	11/28/2018 5:14 PM	[name] Other	Yes
View Subject Eligibility	CDMRP subject_eligibility_screening checklist Version 2 Clean Line.doc	0.02	11/20/2018 4:52 PM	[name] Other	Yes

Document Name	Document	Version	Date Modified By	Uploaded Type	Approved
Checklist					
View Student Screening Interview and Rubric	Student Selection Interview and Rubric 2019 Version 3 Clean.doc	0.05	11/20/2018 4:44 PM	[name] Other	Yes
View Project SEARCH "Recommended" Curriculum Documents (Please note, these are not all used)	2003 PS HS Curriculum.doc	0.03	9/23/2018 4:19 PM	[name] Other	Yes
View Draft Application for Participation	Draft Application for participation Version 3 Redline 10-26-2017.docx	0.06	10/26/2017 12:27 PM	[name] Recruitment/Advertising	Yes
View HRPO IRB Approval	Virginia Commonwealth University Mail - A-19693.a, A-19693.b, A-19693.c, and A-19693.pdf	0.01	1/24/2017 1:59 PM	[name] Ancillary Committee Approval	Not Applicable
View Fort Eustis Business Site for the Research	Virginia Commonwealth University Mail Agreement to be - Re_ [Non-DoD Source] Fwd_ A-the Location and 19693.a, A-19693.b, A-19693.c, and A-19693.pdf	0.01	1/24/2017 1:59 PM	[name] Other	Not Applicable
View York County Public Schools Institutional Investigator Agreement	York VCU_ACE_YCSD Agreement.pdf	0.01	1/24/2017 1:56 PM	[name] Non-VCU site submission form	Not Applicable
View Williamsburg James City County Public Schools Institutional Investigator Agreement	WJCC VCU Project Search 2017 Agreement_W-JCC_Signed.pdf	0.01	1/24/2017 1:55 PM	[name] Non-VCU site submission form	Not Applicable
View New Horizons Regional Education Center Institutional Investigator Agreement	New Horizons Invesitgator Agreement.pdf	0.01	1/24/2017 1:54 PM	[name] Non-VCU site submission form	Not Applicable
View Baseline Demographic Script Clean version 2 11-11-2016	Baseline Demographics Clean version 2 11-11-2016.docx	0.03	11/11/2016 12:55 PM	[name] Research Measure	Yes
View OSP Proposal Review Documentation	OSP Approval_Project Search_Wehman.pdf	0.01	11/1/2016 2:22 PM	[name] Other	Not Applicable
View Grant Attachment 13 Data sharing	NDAR.pdf	0.01	11/1/2016 1:25 PM	[name] Other	Not Applicable
View Grant Attachment 12 Transition Plan	Transition.pdf	0.01	11/1/2016 1:24 PM	[name] Other	Not Applicable
View Grant Attachment 10 Data Collection Instruments Description	1 Instruments Relationship to the Study Objectives.docx	0.01	11/1/2016 1:22 PM	[name] Other	Not Applicable
View Grant Attachment 11	Impact.pdf	0.01	11/1/2016 1:21 PM	[name] Other	Not Applicable

Document Name	Document	Version	Date Modified	Uploaded By	Type	Approved
Impact Statement						
View Grant Attachment 9 Study Management Plan	3 Study Management Plan.docx	0.01	11/1/2016 1:19 PM	[name]	Other	Not Applicable
View Grant Attachment 9 Study Personnel Description	2 Study Personnel Description.docx	0.01	11/1/2016 1:18 PM	[name]	Other	Not Applicable
View Grant Attachment 9 Study Personnel Organizational Chart	1 Organizational Chart.docx	0.01	11/1/2016 1:18 PM	[name]	Other	Not Applicable
View Grant Attachment 8 Data Management	Data_Manage.pdf	0.01	11/1/2016 1:17 PM	[name]	Other	Not Applicable
View Grant Attachment 7 Intervention	Intervention.pdf	0.01	11/1/2016 1:17 PM	[name]	Other	Yes
View Grant Attachment 6 Human Subject Recruitment and Safety Procedures	HumSubProc.pdf	0.01	11/1/2016 1:16 PM	[name]	Other	Yes
View Grant Attachment 5 Statement of Work	SOW.pdf	0.01	11/1/2016 1:15 PM	[name]	Other	Not Applicable
View Grant Attachment 4 Lay Abstract	LayAbs.pdf	0.01	11/1/2016 1:14 PM	[name]	Other	Not Applicable
View Grant Attachment 3 Technical Abstract	TechAbs.pdf	0.01	11/1/2016 1:14 PM	[name]	Other	Not Applicable
View Grant Attachment 2 Intellectual Property	7 Intellectual Property and Sharing of Data.docx	0.01	11/1/2016 1:13 PM	[name]	Other	Not Applicable
View Grant Attachment 2 Letters of Collaboration	3 Hampton City Public Schools.tif	0.01	11/1/2016 1:12 PM	[name]	Other	Not Applicable
View Grant Attachment 2 Letters of Collaboration	2 Newport News.pdf	0.01	11/1/2016 1:12 PM	[name]	Other	Not Applicable
View Grant Attachment 2 Letter of Organizational Support	5 [name] Letter of Support.doc	0.01	11/1/2016 1:11 PM	[name]	Other	Not Applicable
View Grant Attachment 2 List of Relevant Publications	4 List of Relevant Publications.docx	0.01	11/1/2016 1:08 PM	[name]	Other	Not Applicable
View Grant Attachment 2	3 Facilities.docx	0.01	11/1/2016 1:07 PM	[name]	Other	Not Applicable

Document Name	Document	Version	Date Modified By	Uploaded Type	Approved
Facilities					
View Grant Attachment 2 Abbreviations	2 List of Abbreviations.docx	0.01	11/1/2016 1:07 PM	[name] Other	Not Applicable
View Grant Attachment 2 References	1 References.docx	0.01	11/1/2016 1:06 PM	[name] Other	Not Applicable
View Grant Project Narrative	ProjectNarrative.pdf	0.01	11/1/2016 1:05 PM	[name] Other	Yes
View VCU Response to peer and programmatic review	Response to Peer and Programmatic Review Concerns.docx	0.01	11/1/2016 12:16 PM	[name] Other	Not Applicable
View CDMRP Review Notes	CDMRP Review Notes.pdf	0.01	11/1/2016 12:15 PM	[name] Other	Not Applicable
View Newport News Public Schools Institutional Investigator Agreement	Newport News Public Schools_Institutional Investigator Agreement.pdf	0.01	11/1/2016 12:14 PM	[name] Non-VCU site submission form	Not Applicable
View Hampton City Public Schools Institutional Investigator Agreement	Hampton City Public Schools IIA.pdf	0.01	10/3/2016 12:36 PM	[name] Non-VCU site submission form	Not Applicable
View References Cited	References.docx	0.01	9/21/2016 9:16 PM	[name] Other	Not Applicable
View Quality of Life Questionnaire Adult Version	8 qol question adults (1).doc	0.01	9/21/2016 7:56 PM	[name] Research Measure	Yes
View Social Responsiveness Scale 2 - Proxy Report	7 SRS2 Proxy Report.pdf	0.01	9/21/2016 7:56 PM	[name] Research Measure	Yes
View Social Responsiveness Scale 2 - Self Report	6 SRS 2 Self Report.pdf	0.01	9/21/2016 7:55 PM	[name] Research Measure	Yes
View Behavior Assessment Scale in Children Adolescent Ages 12-21	5 30805_BASC3_TRS_A_RS_Form_FNL (1).pdf	0.01	9/21/2016 7:54 PM	[name] Research Measure	Yes
View Support Intensity Scale	4 Support Intensity Scale.pdf	0.01	9/21/2016 7:53 PM	[name] Research Measure	Yes
View 12 and 18 Month Script Version 1 9-21-2016	3 Twelve and Eighteen Months Data script.docx	0.01	9/21/2016 7:52 PM	[name] Research Measure	Yes
View Draft Teacher Recruitment Letter	Letter to teachers recruitment 2016 version 1 9-21-2016.docx	0.01	9/21/2016 7:39 PM	[name] Recruitment/Advertising	Yes
View Draft Treatment Acceptance Letter	Draft Treatment Acceptance Letter version 1 9-21-2016.doc	0.01	9/21/2016 7:37 PM	[name] Recruitment/Advertising	Yes
View Draft Parent/Student Recruitment Letter	Draft Parent Recruitment letter version 1 9-21-2016.doc	0.01	9/21/2016 7:37 PM	[name] Recruitment/Advertising	Yes

Document Name	Document	Version	Date Modified By	Uploaded Type	Approved
View Draft Open House Flyer	Draft open house flyer version 1 9-21-2016.doc	0.01	9/21/2016 7:35 PM	[name] Recruitment/Advertising	Yes
View Draft Control Group Acceptance Letter	Draft Control Acceptance Letter version 0.01 1 9-21-2016.doc	0.01	9/21/2016 7:34 PM	[name] Recruitment/Advertising	Yes
View [name] Biosketch	[name] Bio Sketch.doc	0.01	9/20/2016 4:34 PM	[name] CV/Biosketch	Not Applicable
View [name] Biosketch	biosketch [name].doc	0.01	9/20/2016 4:34 PM	[name] CV/Biosketch	Not Applicable
View [name] Biosketch [name] biosketch (1).doc		0.01	9/20/2016 4:33 PM	[name] CV/Biosketch	Not Applicable
View [name] Biosketch	Bio Sketch [name].docx	0.01	9/20/2016 4:32 PM	[name] CV/Biosketch	Yes

